10. STUDY PROCEDURES

10.1 Methods and Procedures:

We will screen and consent eligible patients of treating physicians at University of Rochester Comprehensive Breast Cancer Center at Pluta Cancer Center.

Consented study subjects will have the option of giving permission for use of their email address in order to send a link to their virtual visit (if subject is not completing the tool in person) or to receive the output from the tool via email.

Participants will complete GA measures (Table 1) and the DPT during a single 30-60 minute study visit either in-person or via virtual visit. In lieu of a post-study interview, our team will utilize the Talk Aloud method with participants while they complete the study assessments and ask the subject follow-up questions after completion of study assessments and the DPT. The Talk Aloud method is designed to identify points of patterns of cognitive thinking, decision making, and problems related to function and language that occur while the participant is engaging with the DPT. Participants will have the option of completing the study during an in-person or virtual visit – this approach is being taken due to COVID precautions to enhance social distancing where able. Slight variations in procedures will be implemented to accommodate an in-person study visit or a virtual study visit. Both scenarios will include the same procedures of completing the GA and the DPT using the Talk Aloud method.

Results that are generated from the Discussion Prioritization Tool will be emailed to the study subject as well as their oncologist. Obtaining permission to send results via email is included during the in-person and verbal consent process.

As for study subjects who complete the DPT virtually, their results will be emailed and screen shared with them via Zoom in order to help them respond to the post study follow-up questions.

10.1.2 In-Person visit:

The study coordinator will familiarize eligible patients to the study by using the following script when approaching for consent.

Coordinator Recruitment Script: The goal of this study is to design a tool that helps patients and oncologists have more personalized discussions about the treatment options for breast cancer. Our hope is that this tool will help make you and your oncologist aware of factors that are important to you when discussing the different treatment options. This tool is not intended to make any decisions for you or to replace discussions that you have with your oncologist regarding your treatment. The online tool will ask questions about your overall health and also will present hypothetical situations about different treatment options. The different treatment options presented are not specific for you or your breast cancer, and are only meant to better understand how you consider the different characteristics between the options.

Once informed consent is obtained in person, patients will meet with a study coordinator either during the same visit or at another time and place based on the patient's preference. When the coordinator meets with the study participant, they will be provided with a tablet to complete the baseline GA measures (table 1).

The following measures are administered to the patient by the study coordinator.

1. Blessed cognitive test
2. Nutritional assessment

The following GA measures are self-reported by the patient:

1. Demographics

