1. PURPOSE OF STUDY

1.1. Overall Goal:

We have developed a Discussion Prioritization Tool (DPT) for older adults considering adjuvant chemotherapy. The DPT utilizes Conjoint Analysis (CA) methodology and the objective of the current study is to assess usability of this DPT in our target population, older adults with breast cancer and to adapt the tool to optimize usability for our target population.

1.2. Study objectives and Hypothesis:

1.2.1. Primary objective:

To evaluate the usability of the DPT in ten older adults considering adjuvant chemotherapy or has made a decision about receiving adjuvant chemotherapy for breast cancer within the past 12 months.

1.2.2. Secondary objective:

To adapt the DPT using “talk aloud” method to optimize usability for our target population.

1.2.3. Hypothesis:

The DPT tool will demonstrate adequate usability in older adults considering adjuvant chemotherapy or has made a decision about receiving adjuvant chemotherapy for breast cancer within the past 12 months.

1.2.4 Usability and feasibility metrics:

The usability and feasibility of the DPT will be evaluated based on the following:

Primary Usability Assessment Measures: System Usability Scale (SUS) (score on 10-item scale, total score ranging 0-100; higher score corresponds to greater usability). We will deem the tool usable if our mean SUS score among the 10 patients enrolled is >68.

Secondary Usability Assessment Measures:

- a) Recruitment rates (percentage of patients who are approached and agree to enroll)
- b) Talk Aloud Method (recordings of patients feedback while using the DPT)

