7.1.6 Subject/Representative Comprehension

The study subject's capacity to participate in the study will be confirmed by their primary oncologist prior to approaching the patient to discuss the study. During the consent process, the subject must be able understand and report the purpose of the study, its procedures, risks, and benefits in order to demonstrate full comprehension of the study.

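### The recruitment script leaves out the usability objective, voices a hope of benefit and does not invite criticism: an avoidable cue before an uncontrolled, subjective rating (low severity, cheap to fix)

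*Combined protocol and SAP*

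**What the plan says.** Section 1.1 treats the tool as finished enough to test: "We have developed a Discussion Prioritization Tool (DPT) for older adults considering adjuvant chemotherapy", and "the objective of the current study is to assess usability of this DPT in our target population". Section 1.2.2 adds the secondary objective: "To adapt the DPT using “talk aloud” method to optimize usability for our target population". Section 1.2.4 gives the decision rule: "We will deem the tool usable if our mean SUS score among the 10 patients enrolled is >68". Section 4.1 describes a single-arm pilot.

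Sections 10.1.2 and 10.1.3 prescribe the same coordinator script for in-person and virtual visits, to be used when the patient is approached for consent. It opens with "The goal of this study is to design a tool that helps patients and oncologists have more personalized discussions about the treatment options" and continues "Our hope is that this tool will help make you and your oncologist aware of factors that are important to you". It also sets limits: "This tool is not intended to make any decisions for you or to replace discussions that you have with your oncologist", and it explains that the treatment options shown are hypothetical.

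Section 7.1.6 requires that, during the consent process, "the subject must be able understand and report the purpose of the study".

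**The concern.** The script's account of the study does not include the primary objective. Patients hear that a helpful tool is being designed and that the team hopes it will help them and their oncologist. They do not hear, in this script, that the tool is being tested for ease of use, that they will be asked to rate it, or that faults are what the team needs to learn about.

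This would matter little in a trial with a comparator arm given the same script. Here the primary measure is a subjective rating with no control, judged by whether the mean of 10 scores passes a fixed line. A favourable cue given to all or most patients would not be removed by averaging. The secondary objective depends on patients saying aloud what does not work, and Section 17 carries those themes forward to a planned randomised trial. Faults left unspoken would go forward with them.

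**Working it through.** **1. The two accounts of the study side by side**

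| Element | Sections 1.1 and 1.2 | Script, 10.1.2 and 10.1.3 |
|---|---|---|
| State of the tool | Already developed | To be designed |
| Primary purpose | Assess usability | Not mentioned |
| Secondary purpose | Adapt the tool | Partly covered by 'design' |
| Expected benefit | Not a study objective | Hope that it raises awareness of what matters to the patient |
| Patient's task of judging the tool | SUS rating and Talk Aloud | Not mentioned |
| Invitation to criticise | Implied by the Talk Aloud aim | Absent |

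The real gap is the missing primary purpose and the missing invitation. The difference between designing and adapting is moderate.

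**2. Order of events**

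The script comes at the approach for consent. The tool, the review of results, the SUS and three open questions follow, in that order. The open request for feedback therefore comes after the SUS has been scored. No visible instruction before the SUS tells patients that negative comments are welcome.

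**3. What a small shift would do**

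The documents give no SUS standard deviation, error rate, power or script effect, so there is no planned figure to reproduce. What follows is an illustration on assumed values.

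- From the documents: 10 items, five response boxes each, total 0 to 100, n = 10, threshold above 68.
- Points per category: five boxes give four steps per item, so 100 / (10 × 4) = 2.5. One category on one item, in every patient, moves the mean by 2.5 points; on two items, by 2 × 2.5 = 5.
- Assumed: true mean 65, SD 10 to 25, common upward shift b of 0, 2.5 or 5 points.
- Formula (normal approximation): P(observed mean > 68) = 1 − Φ((68 − (65 + b)) / (SD/√10)).
- Worked case, SD 10 and b = 2.5: SE = 10/√10 = 3.16; (68 − 67.5)/3.16 = 0.158; P = 0.437.

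| Assumed SD | SE | b = 0 | b = 2.5 | b = 5 |
|---|---|---|---|---|
| 10 | 3.16 | 0.171 | 0.437 | 0.736 |
| 15 | 4.74 | 0.264 | 0.458 | 0.663 |
| 20 | 6.32 | 0.318 | 0.468 | 0.624 |
| 25 | 7.91 | 0.352 | 0.475 | 0.600 |

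The rule is sensitive to shifts of a few points. The table does not show that the script causes one.

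**The case against.** A reader might infer that the script pushes the SUS mean upward and suppresses criticism. The documents do not support that, for these reasons:

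- The stated hope concerns awareness of factors that matter to the patient, not ease of use. Most SUS items in Table 2 ask about complexity, ease, assistance, consistency, learning and confidence, and five of the ten (2, 4, 6, 8 and 10) are negatively worded. Only item 1, on wanting to use the tool often, is plainly open to perceived benefit.
- Hearing that a tool is still being designed may itself invite criticism, so even the direction of any effect is uncertain.
- The rating follows hands-on use, and Section 10.1.2 lets the session take place on another occasion than consent.
- Where the physician makes first contact and takes consent on the same day (Section 7.1, first in-person scenario), the coordinator's script may play little part. A shift common to every patient is not established.
- Critical input is sought elsewhere: Talk Aloud is meant to find problems of function and language, open questions follow, and the SUS form has space for comments.

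A reader might also infer that patients cannot meet the comprehension requirement in Section 7.1.6. That does not follow. The requirement applies during consent, and Sections 7.1 and 7.1.1 describe a consent form, a separate verbal consent script and an information sheet. Their wording cannot be seen here and may state the usability purpose.

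These arguments remove any claim of demonstrated bias. They leave standing that a prescribed script omits the primary objective, includes a favourable sentence that the study does not need, and gives no invitation to criticise. Having the coordinator read out the SUS and record the answers is a more direct route to favourable ratings, but it is a separate matter, and changing it would leave the script as it is.

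**Conclusion.** The point holds as a low-severity improvement. The mismatch with Section 1.1 is a matter of text and is certain. Its effect on the SUS mean or on Talk Aloud comments is a possibility of unknown size and direction, which the consent materials may partly offset. The probabilities above rest on an assumed true mean, SD and common shift; they show only that a mean-above-68 rule with 10 patients has little protection if a shift of a few points occurred. The case for acting rests on the low cost of the change, not on evidence of bias.

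**What to change.** In the scripts in both 10.1.2 and 10.1.3:

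- Replace the opening sentence with: 'We have built an online tool meant to support discussions about breast cancer treatment. This study is to find out how easy or hard it is to use and what should be changed.'
- Replace the sentence of hope with a neutral one: 'The tool produces a summary of the factors that are important to you, which is given to you and to your oncologist.' This keeps patients informed of where their results go.
- Keep the remaining sentences.

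Immediately before the DPT step at every visit, whoever took consent, have the coordinator read: 'We are testing the tool, not you, and critical comments are as useful as positive ones.' Placing it there reaches patients who were consented by their physician and may not have heard the script.

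Cost: a routine amendment, with no added visit or staff. The less persuasive approach might slightly lower the recruitment rate, which is a secondary measure in Section 1.2.4.

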2. IADL
3. Falls history
4. OARS physical health
5. Comorbidity
6. Polypharmacy
7. GDS
8. GAD-7
9. OARS social functioning

Measures administered by the study coordinator will be completed first, then followed by the patient reported measures which will be completed as a component of the tool.

After completing the baseline GA measures, participants will then complete the DPT on the tablet provided by the study staff. Patients will be presented with several scenarios at once (similar to figure 1 above) and asked to select one that is consistent with their preferences. This process will repeat until all attributes are evaluated in the tool. While the subject is completing the DPT, they will be audio recorded in order to collect data for the Talk Aloud method.

After completing the GA and DPT, the summary of the results will be sent to the study email at [contact]. Once the results are emailed, the study coordinator will then show the participant their results on the IPad and will evaluate the patient's impression while they look over their results. We will ask participants to continue with the talk aloud method as they are reviewing the results provided by the conjoint analysis.

The summary of the results that contain a ranking of factors will be provided to the patient's oncologist and the participant will also be provided with their results either in the form of an email sent to their personal email address or in the form of a hard copy print out.

Once results have been provided to the patient, the study patient will then complete a quantitative measure (SUS) evaluating the usability of the tool (Table 2).

The SUS will be administered verbally and the coordinator will have the questions visually available on the IPad for the patient as we go over the questions with them. The study coordinator will record the patient's responses on a hard copy of the SUS form.

Lastly, we will ask additional questions to assess the usability of the tool at the end of the study.

1. Do you have any feedback about the tool?
2. What is your impression of the results in terms of format and understanding?
3. Do you feel that the results accurately reflect your preferences?

10.1.3 Virtual Visit:

The study coordinator will familiarize eligible patients to the study by using the following script when approaching for consent.

Coordinator Recruitment Script: The goal of this study is to design a tool that helps patients and oncologists have more personalized discussions about the treatment options for breast cancer. Our hope is that this tool will help make you and your oncologist aware of factors that are important to you when discussing the different treatment options. This tool is not intended to make any decisions for you or to replace discussions that you have with your oncologist regarding your treatment. The online tool will ask questions about your overall health and also will present hypothetical situations about different treatment options. The different treatment options presented are not specific for you or your breast cancer, and are only meant to better understand how you consider the different characteristics between the options.

Once informed consent is obtained verbally, patients will provide the study coordinator with their email address so that the study team will have the ability to email and provide a link to the GA measures as well as a link enter a Zoom meeting to complete the study procedures. The study coordinator will organize a day and time that works best for the subject to complete the tool.

The following measures are administered to the patient by the study coordinator.

1. Blessed cognitive test
2. Nutritional assessment

The following GA measures are self-reported by the patient:

1. Demographics
2. IADL
3. Falls history
4. OARS physical health
5. Comorbidity
6. Polypharmacy

7. GDS
8. GAD-7
9. OARS social functioning

Measures administered by the study coordinator will be completed first, then followed by the patient reported measures which will be completed as a component of the tool.

Following the baseline GA measures, participants will then complete the DPT during a study visit with the coordinator that is conducted through telehealth platform (e.g. University of Rochester Zoom platform). The link to the DPT will be emailed to the patient so they can open and complete it during the study visit Zoom meeting.

When completing the DPT, patients will be presented with several scenarios at once (similar to figure 1 above) and asked to select one that is consistent with their preferences. This process will repeat until all attributes are evaluated in the tool. Participants will use the talk aloud method while completing the DPT. Feedback given through the Talk Aloud method will be recorded using the secure Zoom record feature during the study visit.

After completing the GA and DPT, the summary of the results will be sent to the study email at [contact]. Once the results are emailed, the study coordinator will then share the results with the participant by using the screen-share feature on Zoom. The study coordinator will evaluate the patient's impression while they look over their results. We will ask participants to continue with the talk aloud method as they are reviewing the results provided by the conjoint analysis.

The summary of the results that contain a ranking of factors will be provided to the patient's oncologist and the participant will also be provided with their results either in the form of an email sent to their personal email address or in the form of a hard copy print out.

Once results have been provided to the patient, the study patient will then complete a quantitative measure (SUS) evaluating the usability of the tool (Table 2).

The SUS will be administered to the patient verbally while displaying the questions by using the screen-share feature on Zoom while we go over the questions with them. The study coordinator will record the patient's responses on a hard copy of the SUS form.

Lastly, we will ask additional questions to assess the usability of the tool at the end of the study.

4. Do you have any feedback about the tool?
5. What is your impression of the results in terms of format and understanding?
6. Do you feel that the results accurately reflect your preferences?

11. AUDIO/VIDEO RECORDINGS

11.1 In Person: Audio Recordings

Audio recordings will be used during in-person study visits in order to collect Talk Aloud data while the study subject completes the conjoint decision-making tool. A secure, handheld recorder will be used to record the subject's feedback. All audio recordings will be uploaded and stored by the research coordinator in a password protected file in Box.

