7.1.4. Duration

Participation in the study will last approximately 60-90 minutes during a one time in-person or virtual visit. If needed, our study team may follow up with the participant for further information for up to 2 months after the initial completion of the study procedures. After the study is completed, participant data will be maintained for 7 years at URMC and will be kept in a password-protected database.

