11.2 Virtual: Video Recordings

Video recordings will be used during virtual study visits in order to collect Talk Aloud data while the study subject completes the conjoint decision-making tool. Video recordings will be

made during a secure virtual visit by using the record function on Zoom to record the subject's feedback. All video recordings will be uploaded and stored by the research coordinator in a password protected file in Box.

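### Would Talk Aloud feedback given in person outside the conjoint task go unrecorded?

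*Combined protocol and SAP*

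**What the plan says.** Section 10.1 sets the scope of Talk Aloud for both visit types: "Both scenarios will include the same procedures of completing the GA and the DPT using the Talk Aloud method". It offers Talk Aloud with follow-up questions as the replacement for a post-study interview. The visit type is the patient's choice: "Participants will have the option of completing the study during an in-person or virtual visit".

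Section 10.1.2 gives the in-person order. The coordinator-administered measures come first, then the patient-reported measures, then the DPT on a tablet with audio recording. The results are then reviewed on the iPad with Talk Aloud still in use. The SUS and three closing questions follow.

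Section 11.1 says that in-person audio recordings are "used during in-person study visits in order to collect Talk Aloud data while the study subject completes the conjoint decision-making tool", and adds: "A secure, handheld recorder will be used to record the subject's feedback".

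For virtual visits, 10.1.3 says: "Feedback given through the Talk Aloud method will be recorded using the secure Zoom record feature during the study visit". Section 11.2 says that video recordings are "used during virtual study visits in order to collect Talk Aloud data while the study subject completes the conjoint decision-making tool".

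Section 1.2.4 lists Talk Aloud as a secondary usability measure and defines it as the recorded feedback of patients working with the DPT. Section 17 codes the Talk Aloud transcripts, transcribes and analyses the answers to the three closing questions, and draws themes from both together.

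**The concern.** Talk Aloud is asked for over a longer part of the visit than the stated in-person recording windows cover. Section 10.1.2 records while the DPT is being completed, and Section 11.1 names only the conjoint tool. The results review comes after both. The patient-reported survey comes before the DPT in 10.1.2, although Section 9 lists it as one of the tool's components. For virtual visits, 11.2 is narrower than 10.1.3.

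Secondary objective 1.2.2 is to adapt the DPT through Talk Aloud, and Section 17 works from transcripts, so speech that is not recorded cannot be coded. The results summary goes to patients and oncologists, so reactions to it matter for the adaptation. If in-person staff recorded only the conjoint task while virtual staff recorded the whole visit, the qualitative material would also differ by visit type, although 10.1 promises the same procedures.

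**Working it through.** The plan gives no figure to reproduce. The check sets the Talk Aloud scope beside the recording statements, step by step.

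| Step | Talk Aloud asked for | In-person recording stated | Virtual recording stated |
|---|---|---|---|
| Coordinator-administered GA | Yes, by the general sentence in 10.1 | Not expressly | 10.1.3 broad enough; 11.2 no |
| Patient-reported survey | Yes, 10.1 | 10.1.2 arguable; 11.1 no | 10.1.3 broad enough; 11.2 no |
| Conjoint task | Yes | Yes, 10.1.2 and 11.1 | Yes, 10.1.3 and 11.2 |
| Results review | Yes, 10.1.2 and 10.1.3 | Not expressly | 10.1.3 broad enough; 11.2 no |
| Three closing questions | Separate follow-up questions | Not expressly, but Section 17 transcribes the answers | Same |

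**Is any step excluded?** No. Neither 10.1.2 nor 11.1 says that recording happens only in its window, and no sentence tells staff to switch the recorder off. The second sentence of 11.1, on recording the subject's feedback, names no step.

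**Does the plan say what Talk Aloud is?** Yes. Section 1.2.4 defines the measure by its recordings. When 10.1.2 asks patients to carry on with Talk Aloud during the results review, the natural reading is that the recorded session carries on too.

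**Is the survey outside the window?** This is doubtful. Section 9 lists the survey as a component of the tool, and 10.1.2 itself says that patients complete those measures within the tool. The same section then places the DPT after the GA. On the first sense, recording during the DPT includes the survey; on the second it does not. Only the results review lies outside the stated window on both.

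**Can the gap be sized?** Not usefully. Let v be the unknown number of in-person visits, 0 to 10.
- Results review only: 1 × v, so 0 to 10 participant steps.
- Adding the survey: 2 × v, so 0 to 20.
- Adding the coordinator-administered GA: 3 × v, so 0 to 30.
- If recording continues while Talk Aloud is in use: 0.

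The count depends on how the visit is divided and which sense of DPT is used. It counts steps without a stated recording window and does not measure data lost.

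**Would results feedback be lost to the analysis?** Not as a whole. Closing question 2 asks about the format and understanding of the results, and question 3 asks whether they reflect the patient's preferences. Section 17 transcribes both and analyses them together with the Talk Aloud material. The coordinator also assesses the patient's impression during the review, and the SUS form has a comments field.

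**Is there a practical reason to stop early?** Little. Section 10.1 describes the GA and DPT as completed "during a single 30-60 minute study visit either in-person or via virtual visit"; Section 7.1.4 says "Participation in the study will last approximately 60-90 minutes". Recording every visit from start to finish would give between 10 × 30 min = 300 min = 5 hours and 10 × 90 min = 900 min = 15 hours in total, on equipment already in use.

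**Is a quantitative result affected?** No. The SUS is read out and its responses are written on a paper form, and the recruitment rate does not use recordings.

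**The case for a change.** The strongest case rests on the results review. It comes after the DPT on any definition, and the three components in Section 9 do not include it. Section 11 is the section devoted to recording, and a coordinator who followed it to the letter would record the conjoint task alone. Unrecorded speech cannot be recovered, an answer given afterwards is not the same as concurrent talk, and clearer wording would cost little.

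Part of this stands. The in-person windows do not expressly include the results review, 11.2 is narrower than 10.1.3, and DPT is used in two senses. The loss, however, needs staff to read a permissive sentence as a restriction, and to stop recording at the point where 10.1.2 has them ask the patient to continue a method that 1.2.4 defines by its recordings. That is an unlikely way to run a 10-patient usability study. Even then, the conjoint task would be recorded at every visit and views on the results would still be transcribed from the closing questions. The virtual wording points to no loss, because 10.1.3 describes recording of Talk Aloud feedback during the visit.

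**Conclusion.** No change to the plan is needed. This is a small unevenness of wording that study staff will fill sensibly: recording during the results review is left unstated, not ruled out. The effect on the primary criterion (mean SUS above 68 in 10 patients) is nil. For the secondary qualitative objective, the worst credible effect is the loss of some concurrent remarks on the results at in-person visits, whose number the documents do not give (0 to 10 of 10). The themes would still rest on the recorded conjoint task and the transcribed closing answers.

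This rests on two assumptions: that staff treat Talk Aloud as a recorded method throughout, as 1.2.4 implies, and that the consent wording, which was not available here, permits recording for that time.
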